### **Columbia Suicide Severity Rating Scale (C-SSRS)**

Suicidality will be assessed using the C-SSRS and summaries will include the incidence of suicidal behavior and suicidal ideation for subjects 6 years of age and older. Scoring of the C-SSRS will be performed as suggested by the C-SSRS Columbia website:

<http://www.cssrs.columbia.edu>.

The following summaries will be presented for the treatment duration (Titration Period and Maintenance Period).

- Number (percentage) of subjects with any treatment-emergent report of suicidal behavior, suicidal ideation, and suicidality (suicidal behavior and/or ideation) will be displayed. A treatment-emergent report of suicidal behavior, suicidal ideation, or

suicidality is an answer of 'Yes' to any question in the respective category during the treatment duration.

- Shift from baseline to the maximum suicidal ideation severity rating (0=no ideation present to 5=active ideation with plan and intent) in the treatment duration will assess worsening of suicidal ideation. Any score greater than 0 indicates the presence of suicidal ideation while a score of 4 (active suicidal ideation with some intent to act) or 5 (active suicidal ideation with specific plan and intent) can be used to indicate serious suicidal ideation.

Descriptive statistics and changes from baseline will be presented by visit for the suicidal ideation intensity score and the suicidal ideation severity rating (treated as a continuous variable) to assess change in suicidal ideation over time. The suicidal ideation intensity score ranges from 0 to 25 and is the sum of the 5 intensity items.

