7. Subjects on antipsychotics or who have psychotic disorder(s) or unstable recurrent affective disorder(s) with a history of attempted suicide within 1 year before Screening Visit (Visit 1)
8. Presence of a progressive central nervous system (CNS) disease, including degenerative CNS diseases and progressive tumors
9. Concomitant use of barbiturates (except for seizure control indication and premedication for EEG) and benzodiazepines (except for seizure control indication) within 8 weeks prior to Visit 2 (Week 0)
10. Use of intermittent rescue benzodiazepines (ie, 1-2 doses over a 24-hour period is considered a 1-time rescue) 2 or more times in the 8 week period prior to Visit 2 (Week 0)
11. Severe renal insufficiency (defined by estimated glomerular filtration rate of <30 mL/min) or subjects who receive hemodialysis
12. Evidence of clinically significant disease (eg, cardiac, respiratory, gastrointestinal, renal disease, hepatic disease) that in the opinion of the investigator(s) could affect the subject's safety or study conduct

NOTE: Stable elevation of liver enzymes, alanine aminotransferase and aspartate aminotransferase due to concomitant medication(s), will be allowed if they are less than 3 times the upper limits of normal.

13. Hypersensitivity to perampanel or any excipients
14. Subjects with rare hereditary problems of galactose intolerance, the Lapp lactase deficiency or glucose-galactose malabsorption
15. Subjects who are participating in other interventional clinical trial
16. Subject who are judged to have inadequate cognitive ability for participation in the study (intelligence quotient [IQ] <80 or investigator judgment)
17. Any suicidal ideation with intent with or without a plan, at the time of or within 6 months of Screening, as indicated by answering "Yes" to questions 4 and 5 on the Suicidal Ideation section of the Columbia-Suicide Severity Rating Scale (C-SSRS)
18. Any lifetime suicidal behavior based on the C-SSRS
19. Concomitant use of any form of cannabidiol (CBD) (revised per Amendment 01)
20. Planned brain surgery during study participation (revised per Amendment 01)

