#### **9.7.1.8.3 COGNITION, DEPRESSION, AND SUICIDALITY**

Cognitive function in subjects 6 years of age and older will be evaluated using EpiTrack. It will be administered at Visits 2, 4, and 7 (Weeks 0, 13, and 52, respectively). Summaries of the proportion of subjects with no/mild/clear cognitive impairment and shifts between these categories from baseline to end of treatment will be produced. The BDI-II will be used to assess depression. Suicidality will be assessed using the C-SSRS and summaries will include the incidence of suicidal behavior and suicidal ideation. The C-SSRS will be administered to patients 6 years of age and older. Subjects under 6 years of age will be clinically monitored for suicidality. (revised per Amendment 01)

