### 5.6.2 Adverse Events

The AE verbatim descriptions (investigator terms from the eCRF) will be classified into standardized medical terminology using the Medical Dictionary for Regulatory Activities (MedDRA). AEs will be coded to the MedDRA (most recent version) lower level term closest to the verbatim term. The linked MedDRA preferred term (PT) and primary system organ class (SOC) are also captured in the database.

A treatment-emergent AE (TEAE) is defined as an AE that emerged during treatment, having been absent at pretreatment (Baseline) or

- Reemerged during treatment, having been present at pretreatment (Baseline) but stopped before treatment, or
- Worsened in severity during treatment relative to the pretreatment state, when the AE was continuous.

Only those AEs that are treatment emergent will be included in summary tables. All AEs, treatment emergent or otherwise, will be presented in subject data listings.

The TEAEs will be summarized using the Safety Analysis Set. The incidence of TEAEs will be reported as the number (percentage) of subjects with TEAEs by SOC and PT. A subject will be counted only once within an SOC and PT, even if the subject experienced more than 1 TEAE within a specific SOC and PT. The number (percentage) of subjects with TEAEs will also be summarized by maximum severity (mild, moderate, or severe).

The number (percentage) of subjects with TEAEs will also be summarized by relationship to study drug (Yes [related] and No [not related]).

The number (percentage) of subjects with TEAEs leading to death will be summarized by MedDRA SOC, and PT. A patient data listing of all TEAEs leading to death will be provided.

The number (percentage) of subjects with treatment-emergent SAEs will be summarized by MedDRA SOC, and PT. A patient data listing of all SAEs will be provided.

The number (percentage) of subjects with TEAEs leading to discontinuation from study drug will be summarized by MedDRA SOC and PT. A subject data listing of all AEs leading to discontinuation from study drug will be provided.

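### The C-SSRS treatment-emergent rule in SAP 5.6.4 has no baseline condition, so the ideation and combined suicidality rows can count ideation that is unchanged or improved since entry

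*SAP*

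**What the plan says.** SAP 5.6.4, under the C-SSRS, plans a table in which the number and percentage of subjects with treatment-emergent "suicidal behavior, suicidal ideation, and suicidality (suicidal behavior and/or ideation) will be displayed". A report is emergent if the answer is yes "to any question in the respective category during the treatment duration". The definition ends there and does not mention baseline. The same section states: "Any score greater than 0 indicates the presence of suicidal ideation".

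A second output is referenced to baseline: "Shift from baseline to the maximum suicidal ideation severity rating". Its stated purpose is to assess worsening of ideation. Changes from baseline by visit are also planned.

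For adverse events, SAP 5.6.2 gives the label a narrower meaning. The event must be absent at baseline, or meet one of two further limbs. The first limb deals with events that come back: "Reemerged during treatment, having been present at pretreatment (Baseline) but stopped before treatment". The second limb deals with ongoing events: "Worsened in severity during treatment relative to the pretreatment state, when the AE was continuous".

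Protocol 9.7.1.8.3 says only that "summaries will include the incidence of suicidal behavior and suicidal ideation". It does not use the term treatment-emergent for the C-SSRS. On entry, exclusion 17 in Protocol 9.3.2 covers "Any suicidal ideation with intent with or without a plan", identified through ideation questions 4 and 5. Exclusion 18 removes anyone with lifetime suicidal behavior on the scale.

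**The concern.** Subjects with ideation below the level of intent are not barred by exclusion 17. If such a subject gives the same answers on treatment as at entry, or milder ones that are still positive, the SAP rule counts a treatment-emergent report. A fall from 3 to 1 is counted in the same way as a rise from 0 to 3.

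The study has no control arm, so no comparator shows how much ideation was carried in from entry. A row labelled treatment-emergent suicidality is naturally read as new, returned or worse on drug, because SAP 5.6.2 defines the term that way for adverse events in the same report. At stake are the content and label of two descriptive safety rows. The retention endpoint is not involved.

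**Working it through.** The plan gives no C-SSRS rate, so there is no figure to reproduce. The check enumerates what the rule counts.

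**Inputs.**
- Severity scale 0 to 5, with any score above 0 meaning ideation is present (SAP 5.6.4).
- Baseline is the last non-missing value before first dose (SAP 8.2.1). The scale is scheduled at Screening and Visit 2 (Protocol Table 4).
- Entry ratings under exclusion 17: 0 to 3 if a yes to either question 4 or question 5 excludes; 0 to 4 if a yes to both is needed, as the wording literally says.
- Assumption: a yes to any ideation question is the same as a maximum on-treatment rating of at least 1.

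**Rules.** Let b be the baseline rating and m the maximum on-treatment rating.
- SAP 5.6.4 counts the pair if m ≥ 1.
- New: b = 0 and m ≥ 1. Worsened: b ≥ 1 and m > b.
- Unchanged: m = b ≥ 1. Improved but still positive: 1 ≤ m < b.

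**Counts.**

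| | b = 0 to 3 | b = 0 to 4 |
|---|---|---|
| All pairs | 4 × 6 = 24 | 5 × 6 = 30 |
| Counted by SAP 5.6.4 | 4 × 5 = 20 | 5 × 5 = 25 |
| New | 5 | 5 |
| Worsened | 4 + 3 + 2 = 9 | 4 + 3 + 2 + 1 = 10 |
| Unchanged | 3 | 4 |
| Improved | 1 + 2 = 3 | 1 + 2 + 3 = 6 |
| Neither new nor worsened | 3 + 3 = 6 | 4 + 6 = 10 |

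Each column adds up: 5 + 9 + 3 + 3 = 20 and 5 + 10 + 4 + 6 = 25. In the first column the six pairs (baseline, maximum) are (1,1), (2,2), (3,3), (2,1), (3,1) and (3,2). The second column adds (4,4), (4,1), (4,2) and (4,3).

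**Comparison with SAP 5.6.2.** The new and worsened pairs meet the adverse-event meaning. The remaining 6 or 10 meet it only where the ideation had stopped before treatment and then returned.

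**Other rows.** The combined row takes in every subject in the ideation row, so it inherits the problem. The behavior row does not: under exclusion 18 an eligible subject has no prior behavior, so any on-treatment report is new. Only a subject enrolled in breach of that criterion could differ.

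**The case against.** The strongest reply is that the SAP already separates the two questions. The incidence rows count any on-treatment yes, which is what the protocol asks for, and the shift table deals with worsening. The label is defined where it is used. Protocol 9.5.1.6.1 also has the investigator review every C-SSRS result and decide whether it is an adverse event. Results judged to be events then fall under the SAP 5.6.2 definition. The SAP nowhere says that 5.6.2 governs the C-SSRS, it refers scoring to an outside website, and the table shells sit in a separate document (SAP Section 11), so titles and footnotes are unknown.

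Much of this stands. It limits the harm and makes this a matter of consistency within one report. It does not change what the stated rule counts, and an explicit definition in the SAP governs over an unseen site. The shift table covers ideation only. Working back from it to a new-or-worsened combined count would require knowing the overlap with behavior and having a baseline rating for every counted subject, so exact recovery cannot be assumed.

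A reader might go further and infer that the rule hides risk, or that every unchanged or improved case is a false positive. The documents support neither. The rule can only add subjects to the count, and some of those cases could be re-emergent in the sense of SAP 5.6.2.

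**Conclusion.** The point holds as a minor correction to descriptive safety reporting. As written, the emergent ideation row and the combined row can include ideation unchanged or improved since entry: 6 of 20 counted pairs with baseline 0 to 3, or 10 of 25 if a baseline of 4 is admitted. The finding that carried-in ideation is counted does not depend on how exclusion 17 is read, because both readings let ratings 1 to 3 through; only the pair counts change.

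It is tempting to read 6 of 20 or 10 of 25 as the share of reported cases that are spurious. The documents do not support that. They give no frequency of entry ideation and no persistence rate, so no percentage of subjects can be stated, and the number affected may be zero.

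The over-count is conservative, the behavior row is essentially unaffected, and worsening of ideation is already shown elsewhere in the plan.

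**What to change.** In SAP 5.6.4, retitle the existing rows *any on-treatment report*, which delivers the incidence the protocol asks for, and refer the reader to the shift table for worsening. That is enough to cure the inconsistency.

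If a treatment-emergent ideation or combined row is kept:
- Count ideation only when it is new, worsened (maximum on-treatment rating above the SAP 8.2.1 baseline), or re-emerged after stopping before treatment, as in SAP 5.6.2. A rule of maximum above baseline alone would omit the re-emergence limb and could under-count.
- State which pre-dose assessment and recall period form the baseline. Exclusion 17 looks back 6 months at Screening. SAP 8.2.1 and 8.2.2 take the latest pre-dose value, normally Visit 2, and no recall period is given for it.
- Show subjects with no baseline rating separately. Entry is from age 4 and the scale from age 6, and the documents do not say whether a child who turns 6 during the study then starts it. SAP 5.3.5.2 plans no special handling of missing data for these variables.
- Leave the behavior rule unchanged.

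The two halves of exclusion 17 should be reconciled by the sponsor, since the range of possible baseline ratings depends on them.

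The cost is a wording change and a small table edit, possibly with a matching edit to the shells. The baseline and maximum ratings are already needed for the shift table; the re-emergence limb also needs a record that ideation had stopped before dosing. The downside is that a narrower count would stand under the emergent label.

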## 5.7 Other Analyses

Not applicable.

## 6 INTERIM ANALYSES

Interim analyses may be conducted at various intervals, depending on the number of accrued subjects.

## 7 CHANGES IN THE PLANNED ANALYSES

Due to recruitment challenges, enrollment was terminated before reaching the planned sample size. Thus, there will not be enough sample size to calculate the 95% CIs. Analysis of BDI-II scale is added as an exploratory analysis.

There are no other changes to the analysis in this statistical analysis plan compared to the protocol. Any future changes to the analysis will be documented separately and will be addressed in the Clinical Study Report.

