#### 9.7.1.6 Efficacy Analyses

This is a study without a control arm. Therefore, formal hypothetical inferences are not necessary, and only descriptive statistics will be performed, as shown below:

For percent change in seizure frequency endpoints:

- Mean, standard deviation, median (95% CIs), minimum, and maximum will be provided.

For responder rate endpoints:

- Number of responders
- Responder rate and its 95% CI

The details for the analyses will be described in the statistical analysis plan.

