#### **9.7.1.6.1 PRIMARY EFFICACY ANALYSIS**

The SAS will be used to summarize retention rate. The retention rate, defined as the proportion of patients remaining on perampanel treatment at 3, 6, 9, and 12 months after initiation of treatment, will be summarized.

The number and percentage of subjects remaining on treatment at each time point and 95% CIs will be summarized.

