### 5.3.4 Examination of Subgroups

All summaries of seizure-related efficacy endpoints will be produced by seizure type (POS, SGS, and PGTCS) and overall. Summaries of retention rate and safety data will be produced by seizure type (POS, SGS, and PGTCS) and overall. All summaries of retention rate and seizure-related efficacy endpoints will also be produced by sex and age group (<12, 12-<=18, 18-<=65, >65).

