## 5.4 Efficacy Analyses

This is a study without a control arm. Therefore, only descriptive statistics will be performed. The SAS will be used to summarize retention rate and the FAS will be used to summarize

seizure data.

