#### 5.4.1 Primary Efficacy Analyses

The retention rate, defined as the proportion of subjects remaining on perampanel treatment at 3, 6, 9, and 12 months after initiation of treatment, will be summarized. The number and percentage of subjects remaining on treatment at each time point will be summarized using SAS. Corresponding 95% CIs may also be presented if allowed by the data.

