#### 5.4.2 Secondary Efficacy Analyses

The FAS will be used to summarize seizure freedom data and conversion data of perampanel as a 1st adjunctive therapy converted to perampanel monotherapy. The number and percentage of subjects who achieved seizure-free status or who converted to perampanel monotherapy will be summarized. 95% CIs may also be calculated if allowed by the data.

The seizure-free status at 3-month in Maintenance Period, at 6-month in Maintenance Period, and during the entire Maintenance Period will only be counted for subjects who complete the respective period. A subject who dropped out early relative to the respective period would be counted as 'No' for seizure-free status in that period.

A subject is considered converted to perampanel monotherapy during Maintenance Period if the subject had a scheduled visit in Maintenance Period and was not taking any concomitant AED at any time during the scheduled visit. A subject who dropped out early before the conversion would be counted as 'No' for conversion status.

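### SAP Section 7 says the sample is too small to calculate the protocol's 95% CIs; for retention (primary) and responder rates that reason is false

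*SAP*

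**What the plan says.** Protocol 9.7.1.6.1 commits to intervals for the primary endpoint: "The number and percentage of subjects remaining on treatment at each time point and 95% CIs will be summarized". The synopsis says the same. Protocol 9.7.1.6 lists "Responder rate and its 95% CI" for the responder endpoints and, for percent change in seizure frequency, "Mean, standard deviation, median (95% CIs), minimum, and maximum will be provided". None of these carries a condition.

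The SAP weakens each one. Section 5.4.1 says of retention: "Corresponding 95% CIs may also be presented if allowed by the data". Section 5.4.3 makes the intervals for percent change and responder rate optional on the same condition. Section 5.4.2 does likewise for seizure freedom and conversion to monotherapy ("95% CIs may also be calculated if allowed by the data"), although the protocol promised no interval for those two.

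SAP Section 7, which records changes from the protocol, reports that recruitment difficulties ended enrolment short of the planned number and concludes: "Thus, there will not be enough sample size to calculate the 95% CIs". The sentence names no endpoint. Neither document gives the number enrolled, a minimum number for an interval, or an interval method.

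**The concern.** Retention and responder rates are single-arm proportions, and early closure of enrolment does not make an interval for a proportion impossible to calculate. The SAP therefore gives a mathematical obstacle as its reason for setting aside a protocol commitment, and for these endpoints there is no such obstacle. The test it relies on, whether the data allow an interval, is never defined.

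What is at stake is the only planned statement of precision for the primary endpoint. There is no control arm, and SAP 5.4 says: "Therefore, only descriptive statistics will be performed". If Section 7 is followed, the retention table shows bare percentages when the shortfall in enrolment has made them least precise. The same would apply to the smaller cells that SAP 5.3.4 adds to the seizure-type split: "All summaries of retention rate and seizure-related efficacy endpoints will also be produced by sex and age group".

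**Working it through.** **Inputs from the documents.** Retention is the proportion of subjects still on perampanel at 3, 6, 9 and 12 months (SAP 5.1.1), with the Safety Analysis Set as denominator (SAP 5.4). Planned enrolment is about 125, with no hypothesis, power or precision target behind it (Protocol 9.7.2; SAP 4). There is thus no sample-size calculation to reproduce, and missing 125 removes no stated condition for an interval.

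**Assumptions.** The achieved n and the retention rate are not given. I use n = 125, 30, 10 and 5, with rates of 60% and 80%.

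**Formulas for x retained out of n.**
- Clopper-Pearson: the lower limit is the 0.025 quantile of Beta(x, n − x + 1), set to 0 if x = 0. The upper limit is the 0.975 quantile of Beta(x + 1, n − x), set to 1 if x = n.
- Wilson, with p = x/n and z = 1.96: centre (p + z²/2n)/(1 + z²/n), half-width z·√(p(1 − p)/n + z²/4n²)/(1 + z²/n).

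Both are defined for every n ≥ 1 and every x from 0 to n. Only n = 0 fails.

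**Results (95%; widths in percentage points, taken before rounding the limits).**

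| x/n | Clopper-Pearson | Width | Wilson | Width |
|---|---|---|---|---|
| 75/125 | 50.9–68.7% | 17.8 | 51.2–68.2% | 16.9 |
| 18/30 | 40.6–77.3% | 36.7 | 42.3–75.4% | 33.1 |
| 6/10 | 26.2–87.8% | 61.6 | 31.3–83.2% | 51.9 |
| 3/5 | 14.7–94.7% | 80.1 | 23.1–88.2% | 65.2 |

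At 80% retention the Clopper-Pearson widths at n = 125, 30, 10 and 5 are 14.7, 30.9, 53.1 and 71.1 points.

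**Extreme cells.** These also have Clopper-Pearson intervals. With x = 0 the upper limit is 1 − 0.025^(1/n), so 0/5 gives 0 to 1 − 0.478 = 52.2%. With x = n the lower limit is 0.025^(1/n), so 5/5 gives 47.8% to 100% and 1/1 gives 2.5% to 100%.

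**Where the reason can hold.** The protocol also plans an interval for median percent change. A distribution-free interval for a median is widest when it runs from the smallest to the largest observation, and its coverage is then 1 − 2(0.5)^n. That is 93.75% at n = 5 and 96.9% at n = 6, so at least 6 subjects are needed to reach 95%. Small seizure-type subsets could fall short. Empty cells, which have no estimate at all, are possible once results are split by seizure type, sex and four age groups (SAP 5.3.4).

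**The case against.** The change is disclosed, with its cause, in the section meant for it. Sections 5.4.1 to 5.4.3 already make the intervals conditional, so Section 7 can be read as declaring that condition unmet. The authors may have meant that the intervals would be too wide to be useful. Counts and percentages remain planned, so a reader can rebuild the interval, and no formal decision depends on it.

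Much of this stands. There is no concealment, no flat contradiction and no bias. The charitable reading does not rescue the sentence, however. It speaks of calculation, which is wrong for a proportion, and width is itself the information the reader needs.

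A second objection concerns breadth. Protocol 9.7.1 plans retention only overall and for POS and PGTCS; the SGS, sex and age splits for retention come from the SAP. Intervals in every SAP cell go beyond the protocol's promise: overall plus three seizure types, two sexes and four age groups make 10 rows, or 40 intervals over four time points. Many could be very wide. That is fair, but the SAP already tabulates percentages in those cells, so adding intervals does no harm.

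Finally, the widths above rest on assumed sample sizes, so the precision lost in this trial cannot be sized. That the interval exists does not depend on those assumptions.

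**Conclusion.** The concern holds and should be fixed. The reason in SAP Section 7 is false for retention and responder rates at any denominator of 1 or more. It can be true only for empty cells, or for an interval on percent change in a very small cell. The fault is an incorrect reason combined with an undefined condition. Its effect is to remove the primary endpoint's only planned measure of precision while leaving the point estimates unaffected.

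As an illustration of scale, at an assumed 60% retention a fall from 125 to 30 subjects roughly doubles the exact interval's width, from 17.8 to 36.7 points. With 10 subjects it is 61.6 points, still calculable and plainly worth showing. The conclusion needs neither the assumed rate nor the assumed n.

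**What to change.** - **SAP Section 7:** replace the sentence with a statement that lower enrolment widens the 95% intervals.
- **SAP 5.4.1 and 5.4.3:** replace the optional wording with a commitment to two-sided 95% intervals by one named small-sample method, for example Clopper-Pearson or Wilson. Cover retention at 3, 6, 9 and 12 months and the responder rates, overall and in each SAP 5.3.4 subgroup with a denominator of at least 1. Show empty cells as not estimable.
- **Median percent change:** give the protocol's interval where the chosen method allows (at least 6 subjects for a distribution-free interval). Otherwise mark it not estimable.
- **SAP 5.4.2:** intervals for seizure freedom and conversion can stay optional, since the protocol does not promise them. If they are kept, define the condition.

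The cost is SAP wording and a programming option, with no new data. The downside is that wide intervals become visible and some small or empty cells are shown as not estimable.
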